15 APPENDICES

APPENDIX A: SCHEDULE OF STUDY EVENTS (SCHEMA)

Days	Screening	Day 1	Day 8	Day 15	Day 22	End of treatment visit	Post-treatment follow-up
Cycles (Dose finding arm)	Before C1	Cycle 1- 12	Cycle 1 only	Cycle 1, 2	Cycle 1 only	N/A	N/A
Cycles (Expansion cohort)	Before C1	Cycle 1- 12	Cycle 1, 4	Cycle 1, 2 and 4	Cycle 1 only	N/A	N/A
Window	Within 4 weeks	+/- 3 days	+/- 3 days	+/- 3 days	+/- 3 days	Within 4 weeks of last treatment	Every 8-12 weeks until 18 months post- treatment, every 6 months thereafter
Infusional therapy (obinutuzumab)		X	Cycle 1 (dose finding), Cycle 4 (expansion)	Cycle 1 (dose finding), Cycle 4 (expansion)			
Physical exam, vital signs, height, weight, performance status, BMI, BSA	X	X	X	X	X	X	X
Collection of AE		X	X	X	X	X	X
CBC, CMP, LDH	X	X	X	X	X	X	X
Beta-2 microglobulin	X	X				X	
Uric acid	X	X					
Hepatitis B and C, HIV serology	X						
Pathology review for eligibility	X						
Pregnancy testing	X	X					
PET whole body lymphoma study	X	Prior to cycle 4 and cycle 7					At 30 months after treatment initiation (CR30)
CT chest, abdomen, pelvis						X	At 18 months after treatment initiation
Oncoplus NGS panel (tumor)	X						
Blood draw for correlative studies	X	Prior to cycle 4, cycle 6				X	At 18 months and 30 months after treatment initiation

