DURATION OF	CC-486: twelve 28-day cycles.	
ADMINISTRATION	Obinutuzumab: nine 28-day cycles. Obinutuzumab will start in cycle 1 in the dose finding arm and on cycle 4 of the expansion cohort.	
STATISTICAL METHODOLOGY	Dose finding: 3+3 design with 3 dose levels and 2 optional dose de-escalation levels.	

Expansion cohort: Simon 2-stage design with 80% power and a type I error rate (α) of 10% to detect a difference in the primary study outcome: $\geq 50\%$ 6-month complete metabolic response (CR) rate indicating an effective combination, versus $\leq 30\%$ 6-month CR rate indicating an ineffective combination.

LIST OF ABBREVIATIONS

ADCC Antibody-Dependent Cellular Cytotoxicity

AE Adverse Event

AESI Adverse Event of Special Interest

AML Acute Myeloid Leukemia

amu Atomic Mass Unit BMI Body Mass Index BSA Body Surface Area

BSD Biological Sciences Division CBC Complete Blood Count

CC-486 Investigational name for oral azacitidine (Celgene Corp.)

CCTO Cancer Clinical Trials Office

CD20 Cluster of Differentiation 20 (B-lymphocyte antigen)

CLL Chronic Lymphocytic Leukemia CR Complete metabolic Remission

CRF Case Report Form

CRA Clinical Research Associate

CRAC Clinical Research Advisory Committee
CTRC Clinical Trials Review Committee

DLT Dose Limiting Toxicity
DNA Deoxyribonucleic acid

DNMT Deoxyribonucleic acid methyltransferase

DOA Delegation of Authority

DSMB Data and Safety Monitoring Board

ECI Event of Clinical Interest

FDA United States Food and Drug Administration

FL Follicular Lymphoma

FLIPI Follicular Lymphoma International Prognostic Index

GELF Groupe d'Etude des Lymphomes Folliculaires

HBcAb Hepatitis B core Antigen HBsAg Hepatitis B surface Antigen

HBV Hepatitis B Virus
HCV Hepatitis C Virus
IB Investigators' Brochure
IDS Investigational Drug Services

IRB Institutional Review Board

IV Intravenous

JC Virus John Cunningham Virus MTD Maximal Tolerated Dose

NADPH Nicotinamide Adenine Dinucleotide Phosphate

NHL Non-Hodgkin Lymphoma
OCR Office of Clinical Research
ORR Overall Best Response Rate

OS Overall Survival
OTC Over the Counter
PD Progression of Disease
PFS Progression-Free Survival
PHI Protected Health Information

PI Principal Investigator

PML Progressive Multifocal Leukoencephalopathy

PO Per Os, Oral PR Partial Response

REDCap Research Electronic Data Capture software

RGU-CHO N-formylguanylribosylurea

RGU Guanlyribosylurea RNA Ribonucleic acid

RP2D Recommended Phase 2 Dose SADR Serious Adverse Drug Reaction

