2.3 SCHEDULE OF EVENTS

For each study visit, basic information including body measurements and vital signs will be recorded. Symptoms of the disease and treatment-related toxicities will be collected and recorded by a licensed medical provider. A physical exam will be performed and documented by a licensed medical provider. Scheduled laboratory assessments will be drawn on the day of the appointment. The assessments and procedures conducted at each visit will follow the study schema shown in **Appendix A.**

The schedule will proceed as follows: first there will be a screening visit within 28 days prior to Cycle 1 to determine eligibility and review the protocol. A 28-day supply of venetoclax and 14-day supply of CC-486 will be given to the patient on Day 1 of each cycle. Cycle 1 will require visits on Day 1, 8, 15, and 22 for treatment, laboratory assessments, and assessment. In the dose-finding cohort only, infusional therapy with obinutuzumab will be given on Cycle 1 Day 1, Cycle 1 Day 8, and Cycle 1 Day 15 in the dose-finding arm. In the expansion cohort, no obinutuzumab will be given in Cycle 1, but the patient will be assessed for toxicity weekly.

Cycle 2 will require visits on Day 1 and Day 15. Infusional therapy with obinutuzumab will be given on Cycle 2 Day 1 in the dose-finding arm only. Cycle 3 through 12 will require visits on Day 1 only in the dose finding arm. The last dose of obinutuzumab will be given on Cycle 9 Day 1 in the dose finding arm. In the expansion cohort, obinutuzumab treatment will start in Cycle 4, with infusions and laboratory studies on Day 1, Day 8, and Day 15; subsequent Cycles through Cycle 12 will include an obinutuzumab infusion on Day 1 only. The end-of-treatment visit will occur within 4 weeks of completion of treatment on Cycle 12, Day 28. Follow-up visits will occur every 8-12 weeks until 18 months post-treatment, and every 6 months thereafter until the close of the trial or disenrollment of the patient.

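### Appendix A marks obinutuzumab on Day 1 of Cycles 1 to 12 in both cohorts, but the text gives Cycles 1-9 (dose finding) and Cycles 4-12 (expansion)

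*Combined protocol and SAP*

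**What the plan says.** Appendix A has two heading rows that list the cycles to which each day column applies, one for the dose-finding arm and one labelled "Cycles (Expansion cohort". In the Day 1 column both rows give Cycles 1 to 12. The row "Infusional therapy (obinutuzumab" has an X in that column with no limit by cycle or cohort. Its Day 8 and Day 15 cells are limited: "Cycle 1 (dose finding), Cycle 4 (expansion". The PET cell in the Day 1 column is limited too: "Prior to cycle 4 and cycle 7".

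Section 2.3 gives the table its standing: "The assessments and procedures conducted at each visit will follow the study schema shown in" Appendix A. The same section then sets out a different obinutuzumab schedule. For expansion: "In the expansion cohort, no obinutuzumab will be given in Cycle 1, but the patient will be assessed for toxicity weekly". For dose finding: "The last dose of obinutuzumab will be given on Cycle 9 Day 1 in the dose finding arm".

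The Study Summary agrees with the Section 2.3 text: "Obinutuzumab will start in cycle 1 in the dose finding arm and on cycle 4 of the expansion cohort", for nine cycles in all. So do Sections 4.2.1.1 (Cycles 1-9, none in 10-12) and 4.2.1.2 (none in Cycles 1-3, then Days 1, 8 and 15 of Cycle 4, then Day 1 of Cycles 5-12).

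**The concern.** A schedule table is what clinic and infusion staff are likely to have in front of them at a visit, and this row is the only dosing row in it. An error in an assessment row costs an extra measurement. An error here is an unplanned 1000 mg antibody infusion.

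The expansion cohort matters most. Its first three cycles are a window in which venetoclax and CC-486 are given alone, so that their effect can be read without that of an anti-CD20 antibody already known to work (Section 1.1.7). The CR rate at the end of that window is a secondary endpoint (Section 2.8). For a patient given obinutuzumab in Cycles 1-3, the month-3 PET could no longer serve that purpose. In the dose-finding cohort the consequence is extra drug in Cycles 10-12. Those cycles fall after the 28-day DLT period, so dose selection by the DLT rules is not touched.

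**Working it through.** This is a count of scheduled infusions. No sample-size or error-rate formula is involved.

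**Inputs.** Each infusion is 1000 mg and each cycle is 28 days. The text schedule comes from Sections 2.3, 4.2.1.1 and 4.2.1.2. The literal schedule comes from Appendix A, with the X applied to every cycle in its column heading.

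**The plan's own figure.** The Study Summary states nine cycles of obinutuzumab. Cycles 1-9 are 9 cycles and Cycles 4-12 are 9 cycles, so the text reproduces that figure in both cohorts. Appendix A read literally gives 12.

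**Cycle-by-cycle lists in Section 5.**
- Cycles 1-3: dose-finding cohort only (5.3.5, 5.4.5).
- Cycle 4: both cohorts (5.5.5).
- Cycles 5-9: no cohort limit, so both (the Cycle 5-9 medication list).
- Cycles 10-12: expansion cohort only (5.7.5).

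These match the text schedule in every cycle. Section 7.4.1.1 also places the first expansion dose on Cycle 4 Day 1.

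**Infusions per patient.**
- Text, dose finding: Cycle 1 Days 1, 8, 15 (3) + Day 1 of Cycles 2-9 (8) = 11.
- Text, expansion: Cycle 4 Days 1, 8, 15 (3) + Day 1 of Cycles 5-12 (8) = 11.
- Appendix A read literally, either cohort: 12 Day 1 infusions + Day 8 + Day 15 = 14.

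**Where the differences fall.**

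| Quantity | Text | Appendix A, literal |
|---|---|---|
| Infusions per patient, each cohort | 11 | 14 |
| Total dose | 11 × 1000 = 11,000 mg | 14 × 1000 = 14,000 mg |
| Expansion, before the PET preceding Cycle 4 | 0 | 3 |
| Expansion, before the PET preceding Cycle 7 | 3 + 1 + 1 = 5 | 6 + 2 = 8 |
| Dose finding, Cycles 10-12 | 0 | 3 |

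The ratio is 14/11 = 1.27, or 27% more drug. The first expansion dose moves from Cycle 4 Day 1 to Cycle 1 Day 1, which is 3 × 28 = 84 days earlier. In dose finding the two schedules are identical through Cycle 9.

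**After correction.** With the Day 1 cell limited to Cycles 1-9 and Cycles 4-12 respectively, the table gives 9 cycles and 11 infusions in each cohort, which agrees with the text.

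**The case against.** The strongest reply is that nobody could be misled for long. The correct schedule appears in the Study Summary, in Sections 2.1, 2.3 and 4.2, and in the Section 5 medication lists. Section 2.3, which sends the reader to Appendix A, gives the right dosing in its next paragraph, and nothing says the table overrides the text. Appendix A is mainly a grid of assessments: venetoclax and CC-486 are not in it, so no patient could be treated from it alone. Its Xs are loose elsewhere, marking height at every visit although Section 5.2.3 limits it to screening, and an end-of-treatment CT that Section 5.8.2 does not require. The literal reading is also odd within its own row, since the Day 8 and Day 15 cells point to a Cycle 4 start in expansion. Finally, weekly teleconferences review protocol adherence (Section 10.1).

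All of this bears on how likely harm is, and it holds the point to minor. It does not make the table right. The authors limited the other two cells of this row and left unlimited the one cell where the cohorts differ most.

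Two smaller points. The table was read from PDF text, so a lost footnote mark on the X cannot be ruled out; none appears, and the neighbouring limits came through intact. The Study Summary's regimen line and Section 4.2.4 place Days 1, 8 and 15 in a first cycle without numbering it. That reads naturally as the first obinutuzumab cycle and does not conflict with the correction.

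**Conclusion.** The concern holds. Appendix A as printed schedules 12 obinutuzumab cycles and 14 infusions per patient, against 9 cycles and 11 infusions in the text. The three extra infusions fall in Cycles 1-3 in expansion and Cycles 10-12 in dose finding.

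These sizes are per patient and conditional on someone dosing from the table instead of the text. How often that would happen cannot be derived from the documents and is probably rare. The conclusion assumes that the X carries no footnote in the original. Figures 3 and 4 (the treatment plans) could not be seen and are not relied on. The severity is minor: an internal contradiction about when a study drug is given, with no effect on the statistical design.

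**What to change.** In Appendix A, replace the X in the obinutuzumab Day 1 cell with: *Cycles 1-9 (dose finding); Cycles 4-12 (expansion)*. The body text already gives this schedule and can stand. The cost is one table cell at the next amendment, with no added patients, visits or analyses.

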APPENDIX C: FOLLICULAR LYMPHOMA INTERNATIONAL PROGNOSTIC INDEX

One point is assigned for each of the following adverse prognostic factors:

- Age > 60 years
- Ann Arbor stage III-IV
- Hemoglobin level < 12.0 g/dL
- Number of nodal areas > 4
- Serum LDH level above normal

Three risk groups are defined: low risk (0-1 adverse factors), intermediate risk (2 factors), and poor risk (≥ 3 adverse factors). Individual risk factors will be reported in this trial at the time of data collection for the pretreatment visit and recorded in REDCap.

APPENDIX D: CONTRACEPTIVE GUIDANCE AND PREGNANCY TESTING

Definition of a Woman of Childbearing Potential (WOCBP): A woman is considered fertile following menarche and until becoming post-menopausal unless permanently sterile (see below)

Women in the following categories are not considered WOCBP:

- Premenarchal
- Premenopausal female with 1 of the following:
 - Documented hysterectomy
 - Documented bilateral salpingectomy
 - Documented bilateral oophorectomy
 Note: Documentation can come from the site personnel's review of the participant's medical records, medical examination, or medical history interview.
- Postmenopausal female
 - A postmenopausal state is defined as no menses for 12 months without an alternative medical cause.
 - A high follicle stimulating hormone (FSH) level in the postmenopausal range may be used to confirm a postmenopausal state in women not using hormonal contraception or hormonal replacement therapy (HRT). However, in the absence of 12 months of amenorrhea, confirmation with two FSH measurements in the postmenopausal range is required.
 - Females on HRT and whose menopausal status is in doubt will be required to use one of the non-hormonal highly effective contraception methods if they wish to continue their HRT during the study. Otherwise, they must discontinue HRT to allow confirmation of postmenopausal status before study enrollment.

Contraception Requirements

Male Participants:

Male participants with female partners of childbearing potential are eligible to participate if they agree to one of the following during the protocol defined time frame:

- Be abstinent from penile-vaginal intercourse as their usual and preferred lifestyle (abstinent on a long term and persistent basis) and agree to remain abstinent
- Use a male condom plus partner use of a contraceptive method with a failure rate of <1% per year as described in Table 8 when having penile-vaginal intercourse with a woman of childbearing potential who is not currently pregnant.
 - Note: Men with a pregnant or breastfeeding partner must agree to remain abstinent from penile-vaginal intercourse or use a male condom during each episode of penile penetration.

Female Participants:

Female participants of childbearing potential are eligible to participate if they agree to use a highly effective method of contraception consistently and correctly as described in the below table during the protocol-defined time frame.

Appendix D Table 1:

Highly Effective Contraceptive Methods That Are User Dependent a

Failure rate of <1% per year when used consistently and correctly.

- Combined (estrogen- and progestin- containing) hormonal contraception ^b
 - o Oral
 - Intravaginal
 - o Transdermal
 - o Injectable
- Progestin-only hormonal contraception ^b
 - o Oral
 - o Injectable

Highly Effective Methods That Have Low User Dependency

Failure rate of <1% per year when used consistently and correctly.

- Progestogen- only contraceptive implant ^b
- Intrauterine hormone-releasing system (IUS)
- Intrauterine device (IUD)
- Bilateral tubal occlusion
- Vasectomized partner

A vasectomized partner is a highly effective contraception method, provided that the partner is the sole male sexual partner of the WOCBP and the absence of sperm has been confirmed. If not, an additional highly effective method of contraception should be used.

Sexual abstinence

Sexual abstinence is considered a highly effective method only if defined as refraining from heterosexual intercourse during the entire period of risk associated with the study treatment. The reliability of sexual abstinence needs to be evaluated in relation to the duration of the study and the preferred and usual lifestyle of the participant.)

Notes:

Use should be consistent with local regulations regarding the use of contraceptive methods for participants of clinical studies.

- a) Typical use failure rates are lower than perfect-use failure rates (i.e. when used consistently and correctly).
- b) If locally required, in accordance with Clinical Trial Facilitation Group (CTFG) guidelines, acceptable hormonal contraceptives are limited to those which inhibit ovulation.

Pregnancy Testing:

WOCBP should only be included in the trial after a negative highly sensitive urine or serum pregnancy test.

Following initiation of treatment, pregnancy testing will be performed whenever an expected menstrual cycle is missed or when pregnancy is otherwise suspected; at the time points specified in the Study Schema (Appendix A), including at the start of each cycle; and as required locally. A positive urine pregnancy test must be followed by a confirmatory serum test.

APPENDIX E: ASSESSING RESPONSE BY LUGANO RESPONSE CRITERIA

Adapted from:

Modified Lugano 5-point scale (5PS)

Score Description

- 1 No uptake
- 2 Uptake \leq mediastinum
- 3 Uptake > mediastinum but \leq liver
- 4 Uptake moderately increased above liver at any site
- 5 Markedly increased uptake above liver at any site
- NE Not evaluable
- X Any areas of uptake not likely to be related to lymphoma

[figure not shown]
Baseline assessment

At baseline, a maximum of six sites with most metabolically active FDG-avid disease (classified as index [or target] lesions) should be selected which, when possible, include the largest lesions most representative of the patient's overall tumor burden. When possible, index lesions should be chosen from disparate regions of the body and include mediastinal and retroperitoneal areas of disease. These lesions must meet the minimum size requirement of being >15 mm in longest diameter (LDi) for nodal disease, or >10 mm in LDi for extranodal lesions. The LDi and shortest diameter should be recorded for each index lesion. All other disease, consisting of up to ten individual or grouped sites, should be selected at baseline as non-index (or non-target) disease. These can include nodal or extranodal lesions or groups of lesions which are not measurable (or measurable beyond the six sites chosen to be followed as index lesions). In addition, non-index disease can include markedly diffuse FDG uptake in the liver or spleen and marked focal FDG uptake in the BM. All selected sites of disease should be followed throughout the course of treatment.

Each designated index and non-index CT lesion should be correlated to the corresponding and corregistered PET lesion. A visual assessment using the 5PS should then be performed on the most metabolically active lesion out of all index and non-index disease. In addition, a quantitative standardized uptake value (SUV) measurement, which represents the maximum SUV (SUV_{max}), should also be documented for this lesion. The SUVmax will be used to calculate the change in uptake compared to post-baseline TPs.

On-study assessment

At each on-study TP, the index and non-index lesions identified at baseline are assessed on the PET/CT exam. The most metabolically active lesion is again assessed using the 5PS approach and the SUV_{max} of that lesion is determined. Of note, it is possible that the most metabolically active lesion identified on-study, when a subject is undergoing treatment, may be different from the most metabolically active lesion which had been identified at the baseline TP. The on-study SUV_{max} measurement is then utilized to perform the on-study response assessment. The response will be recorded for each PET-based disease assessment following the flow diagram in Appendix E, Figure 1.

Appendix E, Figure 1: Flowchart for defining metabolic response. Reproduced from Van Heertum et al. *Drug Des Devel Ther*. 2017.

APPENDIX F: COMMON TERMINOLOGY CRITERIA FOR ADVERSE EVENTS V5.0 (CTCAE)

The descriptions and grading scales found in the revised NCI Common Terminology Criteria for Adverse Events (CTCAE) version 5.0 will be utilized for adverse event reporting (http://ctep.cancer.gov/reporting/ctc.html).

APPENDIX G: ELECTROLYTE IMBALANCES AND PREVENTION OF TUMOR LYSIS SYNDROME

Within the first 24 hours after the first dose or dose increase of any investigational agent in this protocol, if any laboratory criteria below are met, the patient should be hospitalized for monitoring and the investigator notified. No additional doses of investigational agents should be administered until resolution. Following resolution, investigational agents may be resumed following the dose modification guidelines in Section 4.2.2 and Section 4.2.3.

A rapidly rising serum potassium level is a medical emergency.

Guidelines for management are as follows:

- Nephrology (or acute dialysis service) must be consulted/contacted on admission (per institutional standards to ensure emergency dialysis is available).
- IV fluids (e.g., D5 1/2 normal saline) should be initiated at a rate of at least 1 mL/kg/h rounded to the nearest 10 mL (target 150 to 200 mL/h; not 50 mL/h). Modification of fluid rate should also be considered for individuals with specific medical needs.
- Monitor for symptoms or signs of TLS (e.g., fever, chills, tachycardia, nausea, vomiting, diarrhea, diaphoresis, hypotension, muscle aches, weakness, paresthesia, mental status changes, confusion, and seizures). If any clinical features are observed, recheck potassium, phosphorus, uric acid, calcium, and creatinine within 1 hour.
- Vital signs should be taken at time of all blood draws or any intervention.
- The management recommendations below focus on the minimum initial responses required. If a diagnosis of TLS is established, ongoing intensive monitoring and multi-disciplinary management will be per institutional protocols.

Specific recommendations:

Abnormality	Management Recommendations			
Hyperkalemia (including rapidly rising potassium)				
Potassium > 0.5 mmol/L increase from prior value (even if potassium within normal limits)	 Recheck potassium, phosphorus, uric acid, calcium, and creatinine in 1 hour. If further 0.2 mmol/L increase in potassium, but still upper limit of normal (ULN), manage per potassium ULN. Otherwise recheck in 1 hour. Resume per protocol testing if change in potassium is 0.2 mmol/L, and potassium ULN, and no other evidence of tumor lysis. At the discretion of the treating investigator, may recheck prior to hospitalization. If stable or decreased, and still WNL, hospitalization is at the 			

	discretion of the investigator. Potassium, phosphorus, uric acid, calcium, and creatinine must be rechecked within 24 hours.
Potassium > upper limit of normal	 Perform immediate ECG and commence telemetry. Nephrology notification with consideration of initiating dialysis Administer Kayexalate 60 g (or Resonium A 60 g). Administer furosemide 20 mg IV once Administer calcium gluconate 100 to 200 mg/kg IV slowly if there is ECG/telemetry evidence of life-threatening arrhythmias. Recheck potassium, phosphorus, uric acid, calcium, and creatinine in 1 hour. If potassium > ULN 1 hour later, repeat potassium, phosphorus, uric acid, calcium, and creatinine 1, 2, and 4 hours later, if no other evidence of tumor lysis.
Potassium > 6.0 mmol/L (6.0 mEq/L) and/or symptomatic (e.g., muscle cramps, weakness, paresthesias, nausea, vomiting, diarrhea)	 Perform immediate ECG and commence telemetry. Nephrology assessment with consideration of initiating dialysis Administer Kayexalate 60 g (or Resonium A 60 g). Administer furosemide 20 mg IV once. Administer insulin 0.1 U/kg IV D25 2 mL/kg IV. Administer sodium bicarbonate 1 to 2 mEq/kg IV push. If sodium bicarbonate is used, rasburicase should not be used as this may exacerbate calcium phosphate precipitation. Administer calcium gluconate 100 to 200 mg/kg IV slowly if there is ECG/telemetry evidence of life-threatening arrhythmias. Do not administer in same IV line as sodium bicarbonate. Recheck potassium, phosphorus, uric acid, calcium, and creatinine every hour.

Hyperuricemia			
Uric acid > 8.0 mg/dL (476 mol/L)	 Consider rasburicase (dose per institutional guidelines). If rasburicase is used, sodium bicarbonate should not be used as this may exacerbate calcium phosphate precipitation. Recheck potassium, phosphorus, uric acid, calcium, and creatinine in 1 hour. 		
Uric acid > 10 mg/dL (595 μ mol/L) OR Uric acid > 8.0 mg/dL (476 μ mol/L) with 25% increase and creatinine increase > 0.3 mg/dL (0.027 mmol/L) from pre-dose level	 Administer rasburicase (dose per institutional guidelines). If rasburicase is used, sodium bicarbonate should not be used as this may exacerbate calcium phosphate precipitation. Consult nephrology. Recheck potassium, phosphorus, uric acid, calcium and creatinine in 1 hour. If uric acid 8.0 mg/dL 1 hour later, repeat potassium, phosphorus, uric acid, calcium, and creatinine 2 and 4 hours later, if no other evidence of tumor lysis. 		
Hypocalcemia			
Corrected calcium > 7.0 mg/dL (1.75 mmol/L) AND Patient symptomatic (e.g., muscle cramps, hypotension, tetany, cardiac arrhythmias) in the presence of hypocalcemia	 Administer calcium gluconate 50 to 100 mg/kg IV slowly with ECG monitoring. Telemetry. Recheck potassium, phosphorus, uric acid, calcium, and creatinine in 1 hour. If calcium normalized 1 hour later, repeat potassium, phosphorus, uric acid, calcium, and creatinine 2 and 4 hours later, if no other evidence of tumor lysis. Calculate corrected calcium and ionized calcium if albumin is low. 		
Hyperphosphatemia			
Phosphorus > 5.0 mg/dL (1.615 mmol/L) with > 0.5 mg/dL (0.16 mmol/L) increase	Administer a phosphate binder (e.g., aluminum hydroxide, calcium carbonate, sevelamer hydroxide, or lanthanum carbonate).		

	 Nephrology notification (dialysis required for phosphorus 10 mg/dL) Recheck potassium, phosphorus, uric acid, calcium, and creatinine in 1 hour. If phosphorus 5.0 mg/dL 1 hour later, repeat potassium, phosphorus, uric acid, calcium, and creatinine 2 and 4 hours later, if no other evidence of tumor lysis. 		
Creatinine			
Increase > 25% from baseline	 Start or increase rate of IV fluids. Recheck potassium, phosphorus, uric acid, calcium, and creatinine in 1 to 2 hours. 		
$IV = intravenous; \ ULN = upper \ limit \ of \ normal; \ WNL = within \ normal \ limits.$			

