7.4.1 Tumor Lysis Syndrome

Tumor Lysis Syndrome, or TLS, is a known risk for patients with CLL who are treated with high cell killing agents, including venetoclax or obinutuzumab. TLS can be defined either by laboratory criteria or by clinical criteria following the guidelines of (Howard, Jones, and Pui 2011):

- Two of the following laboratory criteria must be present in serum studies in the same 24-hour window from the time of 3 days prior to therapy until 7 days after initial therapy:
 - \circ Uric acid > 8 mg/dL
 - Phosphorus > 4.5 mg/dL
 - o Potassium > 6 mmol/L
 - Corrected calcium < 7 mg/dL or ionized calcium < 4.5 mg/dL
- One of the following clinical criteria is sufficient to diagnose TLS in the 3 days prior to initial therapy or 7 days after initial therapy:
 - Cardiac dysrhythmia at least probably attributable to hyperkalemia
 - Cardiac dysrhythmia, seizure, neuromuscular irritability, hypotension or heart failure at least probably attributable to hypocalcemia
 - Acute kidney injury, defined by increase in serum creatinine level > 0.3 mg/dL from baseline, a single creatinine value > 1.5x the upper age-adjusted limit of normal, or oliguria defined as < 0.5 mL/kg/hr urine production for at least 6 hours

The risk of TLS is expected to be lower in FL than CLL based on prior studies of each agent individually (Davids et al. 2017; Marcus et al. 2017), but the exact nature of the risk of the combination in FL is unknown. Changes in blood chemistry consistent with TLS that require prompt management can occur as early as 6 to 8 hours following the first dose of venetoclax or obinutuzumab. The risk of TLS exists as a continuum based on multiple factors, including tumor burden and comorbidities. Risk is highest for those with bulky disease, elevated leukocyte count, elevated pretreatment LDH levels, compromised renal function, and dehydration. Perform tumor burden assessment with CT scan and CBC with WBC differential, assess blood chemistry (potassium, uric acid, phosphorus, calcium, and creatinine) in all patients and correct pre-existing chemistry abnormalities prior to initiation of treatment with venetoclax or obinutuzumab.

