7.4.1.1 TLS Prophylaxis

In the dose-finding cohort, all patients must receive prophylaxis for TLS before the initiation of the first dose of combination therapy with venetoclax and obinutuzumab on Cycle 1 Day 1.

In the expansion cohort, all patients must receive prophylaxis for TLS prior to venetoclax administration on cycle 1 day 1. Those with high tumor burden, high circulating absolute lymphocyte counts ($> 25 \times 109$ /L), or renal impairment are considered at risk for TLS and must receive

prophylaxis prior to initiation of obinutuzumab on Cycle 4 Day 1 if they are not already on appropriate TLS prophylaxis. For subjects enrolled in the expansion cohort who do not meet those criteria at the time of initiation of obinutuzumab, the need for TLS prophylaxis will be left to the clinical judgement of the treating investigator.

Prophylaxis will include the following:

- Appropriate hydration, consisting of a fluid intake of approximately 2 to 3 L/day starting 24 to 48 hours before the start of treatment.
- Administration of an agent to reduce uric acid (such as allopurinol 300 mg/day orally beginning 72 hours before dose and continuing for 37 days afterwards) or rasburicase IV (for those high risk patients with elevated uric acid levels before treatment, or when otherwise judged to be appropriate by the treating investigator) until normalization of serum uric acid and other laboratory evidence of TLS (e.g., elevated serum LDH levels). Patients with an allergy to allopurinol should receive an alternative TLS prophylaxis regimen such as febuxostat.
- Laboratory results should be reviewed and electrolyte values should not demonstrate any clinically significant abnormalities before the first dose of venetoclax or obinutuzumab, or the patient should receive additional prophylactic treatment and hydration before the initiation of dosing.

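### In Appendix G, the potassium > 6.0 mmol/L row and the upper uric acid row give mutually exclusive instructions, and nothing says which governs when both are met

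*Combined protocol and SAP*

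**What the plan says.** Appendix G sets out what a site does when laboratory values move in the first 24 hours after a first dose or dose increase of any study agent. Three rows of its table matter here.

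- **Upper potassium row.** The trigger is "Potassium > 6.0 mmol/L (6.0 mEq/L) and/or symptomatic". Among its steps: "Administer sodium bicarbonate 1 to 2 mEq/kg IV push. If sodium bicarbonate is used, rasburicase should not be used".
- **Upper uric acid row.** The trigger is "Uric acid > 10 mg/dL", or uric acid above 8.0 mg/dL with a 25% increase and a creatinine increase above 0.3 mg/dL from the pre-dose level. The step is: "Administer rasburicase (dose per institutional guidelines). If rasburicase is used, sodium bicarbonate should not be used".
- **Lower uric acid row.** The trigger is uric acid above 8.0 mg/dL. The step is softer: "Consider rasburicase (dose per institutional guidelines"). The same bar on bicarbonate follows if rasburicase is used.

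On the status of the table, the appendix says: "The management recommendations below focus on the minimum initial responses required". It then leaves ongoing monitoring and multi-disciplinary management to institutional practice once tumor lysis syndrome (TLS) is diagnosed.

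Section 7.4.1 defines laboratory TLS: "Two of the following laboratory criteria must be present in serum studies in the same 24-hour window". Its list includes potassium above 6 mmol/L and uric acid above 8 mg/dL. Section 7.4.1.1 allows, as prophylaxis, "rasburicase IV (for those high risk patients with elevated uric acid levels before treatment", or when the treating investigator otherwise judges it appropriate.

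**The concern.** Each of the two upper rows directs one drug and then rules out the drug that the other row directs. A site whose patient meets both triggers cannot comply with both rows, whichever it follows first. Nothing in Appendix G, in sections 7.4.1 to 7.4.1.3 or in section 4.2.3 says which row takes precedence.

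What is at stake is the clarity of an emergency table in a multicenter trial. TLS of any grade is an adverse event of special interest under section 8.2.5. A site in this position has to set aside one written instruction, and two sites could choose differently without either having a rule to point to.

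**Working it through.** No arithmetic applies: the point does not depend on a sample size, rate or error probability. The check is to take each combination of triggers and ask whether every applicable instruction can be carried out.

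| Combination | Bicarbonate | Rasburicase | Can the text be followed? |
|---|---|---|---|
| Upper potassium row + upper uric acid row | directed by one row, barred by the other | directed by one row, barred by the other | No |
| Upper potassium row + lower uric acid row only | directed | optional | Yes, by not using rasburicase |
| Potassium above the upper limit of normal but not above 6.0 mmol/L and no symptoms, + upper uric acid row | not listed in that potassium row | directed | Yes |
| Upper potassium row after rasburicase given as prophylaxis (7.4.1.1), upper uric acid row not met | directed | already given | Not addressed |

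1. **First combination.** Both rows use the verb *administer* without a condition. The exclusions are conditional on use, but carrying out a row's own instruction satisfies its condition. Following either row therefore breaches the other.

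2. **Second combination.** The table distinguishes *consider* from *administer*, and at uric acid above 8.0 mg/dL alone it uses *consider*. There is no conflict here.

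3. **Fourth combination.** The bar on bicarbonate after rasburicase appears only in the uric acid rows of Appendix G. Section 7.4.1.1 neither repeats it nor refers to it. The text does not say whether the bar reaches back to rasburicase given before treatment. This is an unaddressed sequence, not a pair of simultaneous opposing instructions.

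4. **Link to the venetoclax rule in section 4.2.3.** That section lets venetoclax resume at the prior dose if TLS is diagnosed by laboratory criteria only and resolves within 48 hours. It calls for a reduction if laboratory TLS lasts longer or if TLS is clinical. The second limb of the upper uric acid row needs a creatinine increase above 0.3 mg/dL. Under section 7.4.1, an increase of that size from baseline, within the stated window, is enough for clinical TLS. In that limb the 48-hour clock is generally moot. It could matter only where uric acid exceeds 10 mg/dL and no clinical criterion is met.

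5. **Link to trial results.** TLS is reportable at any grade and whatever its cause (8.2.5), so reporting does not turn on which drug was given. The dose-limiting toxicity definition for grade 3 or 4 non-hematologic events has no duration element (6.2.1). The primary expansion analysis is the 6-month complete response rate (6.2.2).

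**The case against.** The best defence is that this is guidance. The table is presented as management recommendations, and the reciprocal warnings already tell the clinician that the two drugs are alternatives. Nephrology or the acute dialysis service must be contacted on admission, and both rows bring nephrology in. Potassium above 6 mmol/L with uric acid above 8 mg/dL in the same 24 hours, within the stated window, meets laboratory TLS, after which institutional practice takes over.

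Much of this stands, and it limits the point. It does not remove it. The appendix calls these steps the required minimum at the outset, and the hand-over covers ongoing management, not the initial response in which the conflict sits. A nephrology consultation does not tell a site which written instruction it may set aside.

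Three stronger readings are tempting, and the documents do not support them:

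- A reader might infer that every patient with laboratory TLS from high potassium and high uric acid is caught. That is not so: at the 8 mg/dL threshold of section 7.4.1, rasburicase is only to be considered.
- A reader might infer that such patients cannot be treated under the protocol at all. The text shows only that two written instructions cannot both be followed; specialist input and institutional practice remain.
- A reader might infer that prior prophylactic rasburicase creates the same contradiction. The bar is written in the treatment table, and no sentence extends it to prophylaxis.

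**Conclusion.** The point holds in a narrow form. When the upper potassium row and the upper uric acid row are both triggered, Appendix G gives two mutually exclusive instructions and no rule of precedence. That is more than missing detail, because a site meeting both rows cannot obey the table.

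Its size is small. The documents give no frequency for this overlap. Section 7.4.1 expects TLS to be less common in follicular lymphoma than in chronic lymphocytic leukemia and calls the risk with the combination unknown, so no patient count can be drawn from it. Differences between sites are possible but not demonstrated. Sample size, error rates and the primary analysis are unaffected.

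The conclusion rests on reading *administer* as a direction and *consider* as an option, which is how the table itself separates the two uric acid rows. It is a minor safety-text correction, and this review takes no view on which drug or row should prevail.

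**What to change.** At the next amendment the investigators should:

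1. Reconcile the upper potassium row and the upper uric acid row, so that Appendix G gives one consistent instruction when both are met.
2. Clarify whether the bicarbonate exclusion applies to a patient who has already received rasburicase as prophylaxis, and cross-refer between section 7.4.1.1 and Appendix G.

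The clinical content of both statements is for the investigators to decide. The cost is a line or two of protocol text and a cross-reference, with no added procedure, visit or data item.
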